A mobile app informed by the biopsychosocial model of pain that employs a “mind-body” approach was evaluated for quality of self-management support functions specific to chronic pain. Mind-body medicine considers the interactions between the brain and body and considers how emotional, cognitive, and social factors can influence health (e.g., Morone & Greco, 2007). The mind-body app that we explore in the current trial scored the highest of the 19 apps evaluated in both number of self-management functions addressed within the app and scored among the highest in overall app quality as measured by a standardized rating scale (Mobile App Rating Scale) (Devan et al., 2019). To our knowledge, this mobile app has not previously been independently evaluated to determine its efficacy in the treatment of chronic pain. The mind-body app encompasses many of the modalities described above, including

mindfulness training through meditation, CBT through brain training exercises and journaling, and pain education through expert interviews and recorded microlessons. We aimed to investigate the efficacy of the mind-body based mobile app in the treatment of chronic pain using a randomized control trial that involved 6-weeks of regular app usage compared to a usual care, wait-listed control group.

Hypotheses

- i) Participants in the intervention group will report a greater reduction in pain intensity compared to control participants.
- ii) Participants in the intervention group will report improvements in pain catastrophizing, pain interference, and quality of life.
- iii) Changes in pain intensity will be correlated with frequency of app usage.

Objectives:

- i) To investigate the efficacy of a mind-body based mobile app on the experience of chronic pain relative to a waitlisted control group. Outcomes include self-reported measures of pain intensity, perceptions/thoughts about pain, quality of life, and/or functional ability.
- ii) To explore whether frequency of app usage is associated with changes in pain intensity and interference.
- iii) To explore whether changes (if any) in pain intensity and interference persist six weeks post-trial completion.

Primary outcome: Pain intensity as measured using the Brief Pain Inventory (BPI).

Secondary outcomes:

- a. The following additional measures will be compared between the intervention and control group:
 - Pain intensity as measured by the PROMIS Pain Severity short form measures severity over a 7 day time period.

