 - Pain interference as measured by the PROMIS Short Form ((PROMIS Health Organization and Cooperative Group, 2012); (Kean et al., 2016).
 - Pain interference as measured by items in the BPI (Cleeland & Ryan, 1994).
 - Thoughts about pain as measured by Pain Catastrophizing Scale (PCS) score (Sullivan et al., 1995).
 - Quality of life as measured by the short-form (SF)-12 (Ware et al., 1996)
 - Depression, anxiety, and stress as measured by the DASS-21 (Lovibond & Lovibond, 1995).
 - Medication use.
- b. The following exploratory analyses will be performed on the intervention group data:
 - Relationship between all outcomes and frequency of app usage in the intervention group.
 - 12-week follow-up analysis (6 weeks post trial end) to determine whether changes (if any) persist.

Methods

Study Design: This is a parallel group randomized control trial. Participants meeting eligibility criteria at pre-trial self-report screening will be invited to participate in the study. Participants who provide informed consent, complete the baseline data collection, and qualify for study inclusion will be randomized to either an intervention group (mind-body app usage for 6-weeks) or a wait-listed control (usual care). Randomization will be stratified on gender and pain intensity.

Participants

Inclusion: Participants aged 18 to 75 years who have non-malignant chronic or persistent pain. Chronic pain is generally defined as persistent pain that has lasted for more than 3 months (Treede et al., 2015). Our study will include participants that have had ongoing pain for at least 6 months, and participants must experience pain at least half the days in the last 6 months (Deyo et al., 2014). Pain can include bodily pain or head pain (migraine/headache). According to the classifications described above by Treede et al., (2015), our study includes participants with primary chronic pain, head/orofacial pain, visceral pain, post-surgical, and musculoskeletal pain.

Exclusions: The following participants are excluded from participation. Self-reported history of any of the following:

- Psychotic illness or manic episode
- Substance use disorder or problematic substance use within 6 months of start date
- Metastasizing cancers
- Cognitive impairment (that could interfere with using the application)
- Previous experience with the mind-body app under study.

Procedures

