Participants qualifying for study inclusion will be randomized to either an intervention group (mind-body app) or a control group (usual care, wait-listed). Randomization will be stratified on pain intensity on average (from Brief Pain Inventory, item that inquires about pain intensity on average) and gender. We decided to include gender rather than sex for data collection and randomization. Few clinical trials in Canada collect data based on gender, and there are numerous ways that gender may impact pain experience (Boerner et al., 2018; Welch et al., 2017). Randomization method will involve computer-generated block randomization to create varying block sizes of 4 and 8. We will run the trial in cohorts (run in series) with rolling recruitment. First cohort will start the trial October 15th, 2021 (randomized on October 14th, 2021). The anticipated start date for the second cohort is January, 2022 (randomized immediately before cohort start). If we meet our targeted sample size with two cohorts, we will stop recruitment. If we do not have a sufficient sample, we will run a third cohort in Spring, 2022. Data will not be analyzed until the final cohort has complete the 12-week follow-up.

Intervention: Participants in the intervention group will be provided 6-weeks of free access to a mind-body based app. The app includes activities that are evidence-based and informed to treat

the biopsychosocial model of pain. The app is self-directed and includes activities in brain training (cognitive behavioural therapy), meditation, pain education, and expressive writing (journaling). The app also includes links to podcasts that include interviews with scientific experts in chronic pain, pain psychologists, and recovery stories. At the start of the trial participants will be given a brief (<5 min) introductory video to orient them to the app and provide guidelines and tips. Participants will be asked to engage with the app daily or at minimum 4 times per week. A weekly frequency log (during weeks 2, 3, 4, 5, and 6) will be sent to participants via email (with a link to survey monkey) to record number of times they used the app in the previous 7 days. During the trial, participants are asked to continue with usual care for pain treatments (in addition to app usage).

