Control: Participants in the control group will be made aware that they are in the control group as they await access to the app following completion of the trial. They are asked to continue with their usual care for pain treatments over the 6-week trial. A weekly email will be sent to control participants (with a link to survey monkey), to include similar frequency of contact with the research team, and to record any changes (if any) in usual care treatments.

Measures

All participants (control and intervention) will complete baseline questionnaires (detailed below) and a follow-up set of questionnaires at 6 weeks (same as baseline, minus the demographics and pain history sections). All questionnaires and logs will be completed through [surveymonkey.com](https://www.surveymonkey.com). To link pre- and post-surveys along with frequency logs, participants will be given a unique alphanumeric identifier. We will do an additional follow-up survey at 12 weeks in the intervention group. This survey will be similar to the survey at 6 weeks, but will also inquire whether participant continued with app usage.

Measures:

The questionnaires will include the following:

1. Demographics: We will collect data on gender, age, socioeconomic status (education, income), residence, relationship status, dependents, employment status.
2. Pain history: Participants will provide information on their pain condition. This will include location, diagnosis, date of onset, average frequency, changes in employment due to pain. Other details regarding pain are captured in the questionnaires that follow.
3. Brief Pain Inventory Short Form (BPI-SF) - this includes items about location of pain, intensity of pain, current treatments, and interference with daily activities (Cleeland & Ryan, 1994)
4. PROMIS Pain Intensity Scale (Adult Short form) - 3 items (PROMIS Health Organization and Cooperative Group, 2012).
5. PROMIS Pain Interference Scale (Adult Short form) - 8 items (PROMIS Health Organization and Cooperative Group, 2012).
6. Pain Catastrophizing Scale (Sullivan et al., 1995).
8. DASS-21 (Depression, Anxiety, Stress Scale) - 21 items (Lovibond & Lovibond, 1995).
9. QoL questionnaire- SF 12 (Ware et al., 1996).

Data analysis

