Power analysis: We estimated a moderate effect size of $f = 0.3$ (Cohen's $d = 0.6$). A meta-analysis of mobile app-based interventions for the treatment of chronic pain (Pfeifer et al., 2020) reported a small effect at Cohen's $d = 0.4$, but the content of the apps was highly variable and not all included pain education and/or CBT exercises. Another meta-analysis on psychological interventions that included CBT compared to wait-listed controls reported a Cohen's $d = 0.62$ (Hoffman et al., 2007). Using G-power (Erdfelder et al., 2009) calculation with an estimated power of $f = 0.3$, a sample size of $n = 90$ would be required to achieve 80% power (at $alpha = .05$). We aimed to enroll $n = 100$ participants in total.

Statistical analysis: Data will be analyzed using repeated measures analysis of co-variance (ANOVA) with baseline data as a covariate, intervention vs. control as between-group factors, and variable of interest (e.g., pain intensity) as the dependent variable for the primary analysis. It is recommended that randomized controlled trials employ ANCOVA rather than paired t-tests or repeated measures ANOVA (Egbewale et al., 2014).

References

- Berman, R. L. H., Iris, M. A., Bode, R., & Drengenberg, C. (2009). The Effectiveness of an Online Mind-Body Intervention for Older Adults With Chronic Pain. *Journal of Pain*, *10*(1), 68–79. <https://doi.org/10.1016/j.jpain.2008.07.006>
- Boerner, K. E., Chambers, C. T., Gahagan, J., Keogh, E., Fillingim, R. B., & Mogil, J. S. (2018). Conceptual complexity of gender and its relevance to pain. In *Pain* (Vol. 159, Issue 11, pp. 2137–2141). Lippincott Williams and Wilkins. <https://doi.org/10.1097/j.pain.0000000000001275>
- Bujak, B. K., Regan, E., Beattie, P. F., & Harrington, S. (2019). The effectiveness of interdisciplinary intensive outpatient programs in a population with diverse chronic pain conditions: a systematic review and meta-analysis. *Pain Management*, *9*(4). <https://doi.org/10.2217/pmt-2018-0087>
- Cleeland, C. S., & Ryan, K. M. (1994). Pain assessment: global use of the Brief Pain Inventory. In *Annals of the Academy of Medicine, Singapore* (Vol. 23, Issue 2).
- Darnall, B. D., Carr, D. B., & Schatman, M. E. (2017). Ethics forum: Pain psychology and the biopsychosocial model of pain treatment: Ethical imperatives and social responsibility. In *Pain Medicine (United States)* (Vol. 18, Issue 8, pp. 1413–1415). Oxford University Press. <https://doi.org/10.1093/pm/pnw166>

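### No described survey asks about unwanted effects or why app use fell, and no analysis counts participants who worsen, so harm confined to a minority or outside the listed scales would go unreported

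*Combined protocol and SAP*

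**What the plan says.** The combined protocol and SAP describes four follow-up contacts.

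- **Weekly, app arm (Procedures, Intervention):** a log in weeks 2 to 6, sent "to record number of times they used the app in the previous 7 days". Participants are asked to use the app daily, or at least 4 times a week.
- **Weekly, control arm (Procedures, Control):** an email that keeps contact frequency similar and serves "to record any changes (if any) in usual care treatments".
- **Week 6, both arms (Measures):** the baseline questionnaires again, without demographics and pain history. The instruments are BPI, PROMIS intensity and interference, PCS, DASS-21 and SF-12.
- **Week 12, app arm only (Measures):** a similar survey that also asks whether app use continued.

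The listed scales, with medication use, are compared between arms under the primary and secondary outcomes. The named between-arm method is a baseline-adjusted analysis of covariance (Data analysis). Associations of outcomes with frequency of use are planned within the app arm and labelled exploratory. Hypothesis iii concerns the correlation of pain change with use. Under Procedures, no data are analysed until the last cohort has finished its 12-week follow-up.

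**The concern.** The app is self-directed and includes expressive writing, meditation and cognitive behavioural exercises. The introduction says that, to the authors' knowledge, it has not been independently evaluated for efficacy in chronic pain. A first evaluation should be able to say something about unwanted effects as well as benefit. Three gaps stand in the way.

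1. No described item asks about unwanted effects. The weekly contacts also differ in content between arms, so anything volunteered in one arm has no comparable counterpart in the other.
2. No planned analysis counts individuals who worsen. A minority who deteriorate can disappear inside a favourable mean. A participant who worsens and skips week 6 contributes no week-6 score, and no missing-data method is given.
3. A participant who cuts back because the exercises made things worse is recorded only as a low count, like someone who lost interest. Low use with poor pain change then supports hypothesis iii, and harm could be read as a dose-response benefit.

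**Working it through.** **Inputs.** From Power analysis: f = 0.3 (d = 0.6), N = 90 for 80% power at alpha .05, and "We aimed to enroll $n = 100$ participants in total". From Procedures: "computer-generated block randomization to create varying block sizes of 4 and 8". The allocation ratio is not stated; 1:1 is assumed, which those block sizes allow, giving 50 per arm. With 90 completers it would be 45 per arm. No harm rate is given, so every rate below is an assumption.

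**The plan's own figure.** For a two-group F test, lambda = f² × N = 0.09 × 90 = 8.1. Power is 0.804 at N = 90 and 0.799 at N = 89, so N = 90 is reproduced.

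**What the listed scales can show about average harm.** The F test has no fixed direction, so it treats mean worsening as it treats mean benefit. By the normal approximation, power = Φ(d × √(n/2) − 1.96), with n = 50 per arm and √25 = 5:

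| Mean worsening | Calculation | Power |
|---|---|---|
| 0.6 SD | Φ(3.0 − 1.96) | 85% (84% by F test) |
| 0.4 SD | Φ(2.0 − 1.96) | 52% |
| 0.2 SD | Φ(1.0 − 1.96) | 17% |

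The unadjusted 95% CI half-width is 1.96 × √(2/50) = 0.39 SD, or 0.41 SD with 45 per arm.

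**What a mean can hide (illustration only).** Suppose 10% of the app arm worsen by 1 SD and 90% improve by x. Then 0.9x − 0.1 × 1 = 0.6 gives x = 0.7/0.9 = 0.78 SD. The net effect equals the planned benefit.

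**What one added item would give.**
- With zero events among n, the one-sided 95% upper limit is 1 − 0.05^(1/n): 5.8% for n = 50 and 6.4% for n = 45.
- The chance of at least one event among 50 is 1 − (1 − p)^50: 39% at p = 1%, 64% at 2% and 92% at 5%.
- Power for an excess over control at 50 per arm (two proportions, normal approximation, two-sided .05):

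| Control vs app | Power |
|---|---|
| 5% vs 10% | 16% |
| 5% vs 15% | 38% |
| 5% vs 20% | 62% |
| 5% vs 25% | 81% |
| 10% vs 20% | 29% |

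**The case against.** The strongest reply is that harm is already measured. DASS-21 asks both arms about depression, anxiety and stress at baseline and week 6, and the pain, catastrophizing and quality-of-life scales can all move in the harmful direction. This stands. A reader might infer from the missing item that the trial cannot detect or rule out harm, or that nobody is asked about distress. The documents do not support either inference: a mean worsening of 0.6 SD is as detectable as the planned benefit. Nor is it right that no bound could be given without a new item. The surveys are linked by participant, so the proportion whose scores worsen, with a confidence limit, can be computed from data already planned. What is missing there is a prespecified table.

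Three further replies also stand. Not every planned comparison is a mean, since usage associations are planned and medication use has no stated metric. The zero-event limit is optimistic, because some positive answers to a question about new or worsened symptoms are likely in chronic pain; the between-arm contrast matters more, and its power is low. And the mixture is invented; a similar one could be built for any trial that compares means.

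The absence must also be stated with care. One passage and the consent pages were removed before review, survey items are not shown, and the Measures list jumps from item 6 to item 8. Safety reporting could be described in text not seen.

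None of this covers unwanted effects outside the scales, a minority who worsen, or the reason for low use.

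**Conclusion.** The point holds in a limited form. On the text available, no described survey asks about unwanted effects or reasons for reduced use, the weekly contacts are not comparable between arms, and no analysis counts individual worsening. Sizeable average worsening on the listed scales can be detected at week 6 (about 84-85% power for 0.6 SD, 50 per arm, 1:1 assumed). Harm outside those scales, or confined to a minority, would go unreported. Low use because of worsening cannot be separated from loss of interest when the usage correlation is interpreted; that analysis is exploratory, which limits the damage but does not remove the ambiguity.

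A reader might also infer that the history-based exclusions should be asked again during follow-up. The documents give no ground for calling that a defect: those items are stated as eligibility criteria.

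This should be changed because it is cheap and alters what the trial can say about safety. It does not undermine the primary efficacy comparison.

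**What to change.** 1. Add one identical, neutrally worded item with a free-text line to the weekly and week-6 surveys of both arms, asking about new or worsened symptoms or unwanted experiences. Name a role on the existing team to read the answers on receipt, since no data are analysed until the last 12-week follow-up.
2. In the app log, when use falls below the requested 4 times a week, add a tick-box for the reason, including 'made me feel worse'.
3. Report by arm, with confidence intervals, the number reporting an unwanted effect and the number whose BPI intensity and DASS-21 worsened from baseline by a margin fixed in advance. State the number assessed in each arm.
4. Report the reasons for low use descriptively beside the hypothesis iii correlation, and state that the correlation is not causal. Do not re-run it after excluding those who felt worse: that selects on a post-randomisation variable tied to outcome and would preferentially remove poor results.

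The cost is one or two items on surveys already being sent and one descriptive table. Surveys become slightly longer, and some reports will be non-specific in this population; the identical control-arm item puts those in context. The report should say that the item supports a rate and a contrast, and that the 5.8% limit (6.4% with 45) applies only if no events are reported.

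### Baseline PROMIS pain intensity is collected from everyone but not specified as a covariate in the primary model; adding it may give a small precision gain at almost no cost

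*Combined protocol and SAP*

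**What the plan says.** The protocol names BPI pain intensity as the primary outcome and does not say whether this is one item or a composite. The list of secondary outcomes adds a second intensity measure: "Pain intensity as measured by the PROMIS Pain Severity short form measures severity over a 7 day time period". It appears again in the questionnaire list under Measures as "PROMIS Pain Intensity Scale (Adult Short form) - 3 items".

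Measures also states who fills in the baseline set: "All participants (control and intervention) will complete baseline questionnaires (detailed below"). Under Study Design, participants are randomised only after completing baseline data collection. The PROMIS score is therefore measured before allocation in both arms and should be available for everyone randomised.

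The Statistical analysis paragraph specifies an ANCOVA "with baseline data as a covariate, intervention vs. control as between-group factors, and variable of interest (e.g., pain intensity) as the dependent variable". It does not name the baseline measure. The natural reading is the baseline value of whichever outcome is being analysed, which for the primary outcome is baseline BPI. PROMIS is not mentioned as a covariate anywhere.

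**The concern.** The protocol chose ANCOVA deliberately, so baseline adjustment is already its way of gaining precision. The more of the week-6 variation the baseline covariates explain, the narrower the confidence interval for the treatment effect. A second baseline score aimed at the same construct may explain some variation that baseline BPI misses, particularly in a population that may have pain on as few as half of days. If it does, the primary interval will be wider than the collected data require.

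What is at stake is modest precision, not validity. Precision matters somewhat more if the true effect is near d = 0.4, which the Power analysis paragraph reports for app-based interventions, than at the d = 0.6 it adopts.

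**Working it through.** **1. The plan's own figure.** Inputs from the Power analysis paragraph: f = 0.3 (d = 0.6), alpha 0.05, 80% power, total N = 90. Equal allocation is assumed. A noncentral F test with two groups gives power 0.799 at N = 89 and 0.804 at N = 90, so N = 90 reproduces. That calculation takes no credit for any covariate.

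**2. Gain from a second baseline score.** Let r1 be the correlation of baseline BPI with week-6 BPI, r2 that of baseline PROMIS with week-6 BPI, and r12 that between the two baselines. The documents give none of these; all values below are assumptions.

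- BPI only: R² = r1²
- Both: R² = (r1² + r2² − 2·r1·r2·r12) / (1 − r12²)
- Gain, as a share of sample size: (1 − R² BPI only) / (1 − R² both) − 1

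Worked case 0.5/0.5/0.7 (r1/r2/r12): R² both = (0.25 + 0.25 − 0.35)/0.51 = 0.294. The gain is 0.75/0.706 − 1 = 6.2%. The confidence interval shrinks by a factor of √(0.706/0.75) = 0.97, so it is about 3% narrower.

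| r1/r2/r12 | R² BPI only | R² both | Gain |
|---|---|---|---|
| 0.5/0.4/0.8 | 0.250 | 0.250 | 0.0% |
| 0.5/0.4/0.7 | 0.250 | 0.255 | 0.7% |
| 0.5/0.45/0.8 | 0.250 | 0.257 | 0.9% |
| 0.5/0.45/0.7 | 0.250 | 0.270 | 2.7% |
| 0.5/0.5/0.8 | 0.250 | 0.278 | 3.8% |
| 0.5/0.5/0.7 | 0.250 | 0.294 | 6.2% |
| 0.5/0.55/0.7 | 0.250 | 0.328 | 11.7% |

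**3. Cost of the extra covariate.** The expected variance rises by about 1% (a factor of 96/95 at 100 participants, 86/85 at 90). In the zero-gain row the net effect is therefore about −1%; power at d = 0.4 with 90 analysed stays at 0.582 to three decimals.

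**4. Power with 90 analysed.** Noncentrality = N·(d/2)²/(1 − R²), with d in unadjusted SD units, for the case 0.5/0.5/0.7.

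- d = 0.6: 8.1/0.75 = 10.8 with BPI only, 8.1/0.706 = 11.5 with both. Power goes from 0.90 to 0.92.
- d = 0.4: 3.6/0.75 = 4.8 with BPI only, 3.6/0.706 = 5.1 with both. Power goes from 0.58 to 0.61.

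**5. Sensitivity to the assumptions.** Let r1 run over 0.4-0.6, r2 over 0.5-0.65 and r12 over 0.6-0.8, in steps of 0.05. The gain then runs from 0.2% (0.6/0.5/0.8) to 56% (0.4/0.65/0.8), and the rise in power at d = 0.4 from 0.1 to 19 points. The top end arises only where PROMIS predicts week-6 BPI far better than BPI's own baseline does. The answer depends mainly on how r2 compares with r1.

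**The case against.** The strongest reply is that nothing here is wrong. ANCOVA on the outcome's own baseline is standard and unbiased, N = 90 reproduces, and with r1 = 0.5 that model already gives about 90% power at the planned effect. All of this stands.

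Nor do the documents show that PROMIS adds anything. BPI's own baseline shares its items and scale with the outcome and could well be the better predictor, in which case the gain is close to zero. The argument that baseline BPI is noisy is also limited: the BPI item used for stratification asks about pain on average, not pain at one moment. This stands too, and it is why the gain can only be given as a conditional range.

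Three stronger readings are tempting and are not supported:

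- A reader might infer that the plan forgoes a definite amount of precision, such as 4-20% of the sample size. Such a range follows from particular correlations with PROMIS at least as predictive as BPI. Of the 100 grid points in the sensitivity check, 49 fall outside it.
- A reader might infer that the PROMIS baseline is excluded from the primary model. The text leaves the covariate unnamed, so the accurate statement is that PROMIS is not specified.
- A reader might take 58% as the trial's power. It holds only at d = 0.4, which the plan discusses and, with a stated reason, does not adopt. Whether d = 0.6 is optimistic is a separate question.

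What remains is that the possible loss from adding PROMIS is about 1% in variance and the possible gain is several times that.

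**Conclusion.** The point holds as an optional improvement of low severity. A pre-randomisation pain intensity score is available for both arms, the primary model does not specify it, and including it may narrow the primary confidence interval. The planned model is valid without it.

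The size is unknown from the documents. With r1 = 0.5 and r12 between 0.7 and 0.8, it is about 0-3% of the sample size if PROMIS is the weaker predictor by 0.05 to 0.10, about 4-6% if the two are equal, and more if PROMIS is stronger. Other assumed correlations move these figures. In the central case power rises by roughly 2 to 3 percentage points.

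**What to change.** State the primary model as week-6 BPI pain intensity regressed on arm, baseline BPI pain intensity and baseline PROMIS pain intensity. Fix this before any outcome data are analysed. The Procedures section leaves room for it, because analysis waits until the final cohort has completed the 12-week follow-up. Naming the covariates also removes a later choice between one baseline score and two.

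The cost is one sentence and one degree of freedom, with no new data. Adjusting the PROMIS intensity and pain interference outcomes for paired baselines in the same way is optional; no calculation here supports it.
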